#### **Randomization and Arm Assignment**

Randomization will be done at the time of enrollment by the Central Registration Office, which will perform the randomization using randomization assignments determined by the study statistician. Subjects will be randomized to one of two treatment arms: low dose (0.5 mg/d) and high dose (0.5, escalating every two weeks to 1.0. 1.5 or 2.0 mg/d) pomalidomide. If one of the arms closes due to futility, toxicity or completion, enrollment will continue to the remaining arm.

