# **10 STATISTICAL CONSIDERATIONS**

It is known from prior trials that the pomalidomide MTD is about 3 mg/d in persons with bone marrow disorders receiving therapies for cancer. Due to high frequency of pomalidomide dose de-escalation observed in preliminary cGvHD experiences when given at 3 mg/d, this study will explore clinical toxicity of gradual escalation doses below 3.0 mg.

The primary objective of this study is to determine if patients with cGVHD will experience an acceptable level of clinical response when treated with either a constant low dose of pomalidomide (0.5 mg/day) for six months or a strategy of increasing dose of pomalidomide from 0.5 mg/d up through each individual patients' maximum tolerated dose, with escalations by

0.5 mg/d every 2 weeks to a maximum of 2.0 mg/d. The study will thus randomize patients between fixed low dose and escalating dose to tolerance, and will be considered a randomized phase II trial with a selection design component.

In each of the two arms, the trial will be conducted using a single stage design. With 16 patients on each arm, an exact binomial test would have 90% power to detect a difference between a 5% response rate and a 30% response rate using a 0.10 one-sided significance level and an exact binomial test. In addition, after the trial has ended, the 80% and 95% confidence limits will be determined for each arm about the observed response proportion in order to aid in interpretation of the results. If there are 3 or more responses in 16 patients, this would be sufficient to rule out a 5% response rate and demonstrate consistency with 30% or better response rates.

At the conclusion of the study, if both arms are able to accrue to the full 16 patients, the arm with the greater number of responses will be selected for further investigation subsequently. That is, if the fixed, low-dose arm, or the increasing dose level arm, has the greater number of responses, then that arm would be studied further. In the event of a tie, the lower dose arm would likely be preferred. As an example, if the true probabilities of response on the two arms were 0.10 and 0.30, then the probability of correctly selecting the superior arm would be 93%, and if the true probabilities on the two arms were 0.15 and 0.30, the probability of correct selection would be 84%.

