As an early stopping rule for futility, if after 7 patients have enrolled on either arm, 0 have responded, then no further patients will be accrued to that arm as soon as this can be determined. In practice, this means that patients may continue to be accrued beyond 7 in an arm, but no more patients would be registered and treated on that arm once the first 7 were evaluated and no PRs or CRs were identified in those first 7.

To protect patient safety, an early stopping rule will be implemented as follows. For patients treated on either arm, if 2 patients in the first 6, or 33% of the patients at any time experience a DLT at a given dose level, no further patients will be treated at that given level on the trial. Furthermore, when more than 6 patients have received a given dose level, if at any time 33% or more patients experience a DLT when treated at that dose level, then no further patients will be treated at that dose level. Thus, as an example, should there be 2 patients with a DLT in the first 6 who are able to receive 2.0 mg/day on the dose escalating arm, then subsequent patients treated on that arm will not be escalated beyond 1.5 mg/day.

With two arms, each of which has a maximal accrual of 16 patients, up to 32 evaluable patients will be randomized. In order to allow for a very small number of patients who are not able to be evaluated at all for response, the accrual ceiling will be set at 35.

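### The 93% and 84% correct-selection probabilities leave out the 0-of-7 futility stop, and section 10 does not say what is selected when one arm closes early

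*Combined protocol and SAP*

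**What the plan says.** Section 10 (Statistical Considerations) gives each arm a single-stage design and then adds a selection rule: "if both arms are able to accrue to the full 16 patients, the arm with the greater number of responses will be selected". On ties it says: "In the event of a tie, the lower dose arm would likely be preferred". The examples follow in the same paragraph. The first, put at 93%, reads: "if the true probabilities of response on the two arms were 0.10 and 0.30, then the probability of correctly selecting the superior arm would be". The second, with true rates of 0.15 and 0.30, is put at 84%.

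The next paragraph of section 10 adds a futility stop to each arm. Accrual may run past 7 while the first 7 are being evaluated. The limit is then stated as follows: "no more patients would be registered and treated on that arm once the first 7 were evaluated and no PRs or CRs were identified". Section 2.5 (Randomization and Arm Assignment) adds: "If one of the arms closes due to futility, toxicity or completion, enrollment will continue to the remaining arm".

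Neither section says which arm, if any, is selected once an arm has closed for futility. Neither says whether the 93% and 84% allow for the stop.

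**The concern.** The selection probabilities stand beside a design with a futility stop but appear to be computed without one. At the response rates in the examples the stop is far from rare: a true 0.10 arm has close to an even chance of no responses in 7 patients. The superior 0.30 arm can also be closed this way, and then it cannot be chosen.

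Choosing which regimen to study further is the trial's only comparative output. If the printed chance of choosing correctly belongs to a design without the stop, readers are given a figure that the written design may not deliver. The silence about the one-arm case also leaves the decision to be made after the data are seen.

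**Working it through.** **Inputs.** 16 patients per arm, true rates 0.10 against 0.30 and 0.15 against 0.30, selection by the larger count, and low dose likely preferred on ties (all section 10). Closure at 0 responses in the first 7 (section 10). Arms are taken as independent, with the same response rates used for futility and for selection.

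**Step 1: reproduce the printed figures.** Let S and I be independent Binomial(16, p) counts for the superior and inferior arms, with no stop.

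| Quantity | 0.10 vs 0.30 | 0.15 vs 0.30 |
|---|---|---|
| P(S > I) | 89.4% | 79.5% |
| P(S = I) | 6.3% | 10.1% |
| P(S > I) + ½·P(S = I) | 92.5% | 84.5% |
| P(S > I) + P(S = I) | 95.7% | 89.6% |
| Normal approximation | 92.8% | 84.9% |
| Printed | 93% | 84% |

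The split-tie count matches both printed figures to within about half a point, and the normal approximation to within a point. Both use 16 per arm and no stop. The per-arm test also reproduces: 3 or more responses in 16 gives a one-sided level of 0.043 at 5% and power of 0.901 at 30%. The plan's arithmetic is therefore sound for the situation it describes.

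**Step 2: how often the trigger is met.** P(0 of 7) = (1 − p)^7.

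- 0.9^7 = 47.8%, 0.85^7 = 32.1%, 0.7^7 = 8.2%.
- Both arms pass: (1 − 0.478)(1 − 0.082) = 47.9%, and (1 − 0.321)(1 − 0.082) = 62.3%.
- At least one arm triggers: 52.1% and 37.7%.
- Inferior arm alone: 43.9% and 29.4%. Superior arm alone: 4.3% and 5.6%. Both arms: 3.9% and 2.6%.

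**Step 3: correct selection with the stop fully binding.** Enumerate each arm's count jointly with at least 1 response in its first 7.

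| Quantity | 0.10 vs 0.30 | 0.15 vs 0.30 |
|---|---|---|
| a. Both reach 16, superior ahead | 41.5% | 48.0% |
| b. Both reach 16, tied | 3.9% | 7.3% |
| c. Inferior closed, superior open | 43.9% | 29.4% |
| Given both pass: (a + ½b) / P(both pass) | 90.7% | 82.7% |
| Lone survivor selected: a + ½b + c | 87.3% | 81.0% |

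If a lone survivor must also have 3 or more of 16, c is replaced by P(inferior closes) × P(superior passes and has 3 or more). The second factor is 0.856. That gives 43.4% + 0.478 × 0.856 = 84.4%, and 51.6% + 0.321 × 0.856 = 79.0%, where 43.4% and 51.6% are a + ½b.

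**Step 4: ties to the low-dose arm.** Drop ½b if the escalating arm is superior; add a further ½b if the low-dose arm is superior.

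| Rule for a lone survivor | Superior arm | 0.10 vs 0.30 | 0.15 vs 0.30 |
|---|---|---|---|
| Selected | Escalating | 85.4% | 77.4% |
| Selected | Low dose | 89.2% | 84.6% |
| Needs 3 or more of 16 | Escalating | 82.5% | 75.4% |
| Needs 3 or more of 16 | Low dose | 86.3% | 82.7% |

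**Step 5: over-run.** The endpoint is read at 6 months (section 3.1). To fill before its seventh patient is evaluated, an arm needs 9 more patients in about 6 months, or 1.5 per month, which is 3 per month over two arms. Section 2.1.3 gives about 3 per month for the main feeder protocol, with other referrals allowed. That is not this trial's own accrual rate, which the documents do not give. If both arms fill first, the stop has no effect and the results return to 92.5% and 84.5%.

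**The case against.** The strongest reply is that section 10 makes the selection rule conditional on both arms reaching 16, and that the figures follow as an example of that case. On that reading they illustrate the rule and are not operating characteristics of the whole design. Given that both arms pass futility, the exact values are 90.7% and 82.7%, only about 2 points below the no-stop values. This largely stands: the figures are close to the rule they illustrate, and there is no arithmetic slip. But the text presents them simply as the probability of correct selection, without that qualification.

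Three stronger readings are tempting, and the documents do not support them.

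- A reader might infer that an arm is cut short in 52% and 38% of trials. Those are chances of meeting the trigger. Section 10 lets accrual pass 7 while evaluation is pending, so some arms that meet it may already be full. Most of the total (44 and 29 points) is the inferior arm closing alone, which favours the superior one.
- A reader might infer that the plan selects nothing in about half of trials like the first example. The plan is silent on that case; it does not rule selection out. Section 2.5 keeps the remaining arm enrolling, and section 10 gives each arm its own criterion of 3 or more responses in 16.
- A reader might infer that the printed figures are too high under every convention. With ties to a superior low-dose arm and the survivor selected, the second example gives 84.6%, which is not below 84%.

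**Conclusion.** The point holds in limited form. The 93% and 84% are right for 16 per arm, no futility stop and ties split evenly. They are not the figures for the design with its stop, and the selection rule does not cover a trial in which one arm closes.

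With the stop fully binding and ties split, the loss against the exact no-stop values is 5.2 points (92.5 to 87.3) and 3.5 points (84.5 to 81.0) if the survivor is taken forward. It is 8.1 and 5.5 points if the survivor must also reach 3 of 16. The loss disappears if both arms fill before the stop can act. The tie convention matters by a similar amount: section 10 leans towards the low dose, whereas the printed figures need ties split.

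These results assume independent arms and one response definition throughout. Section 10 counts only PR and CR for futility, while sections 3.1 and 6.2.2.1 also count stable disease as response in patients progressing at entry. If the 0.10, 0.15 and 0.30 rates include such patients, the trigger would be met more often than computed. The dose-level toxicity stop is not modelled.

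**What to change.** In section 10, state what is selected when one arm closes for futility and when both do. Then replace 93% and 84% with the probabilities for that rule, including the stop: with ties split, 87% and 81% if the surviving arm is simply selected, or 84% and 79% if it must have 3 or more responses in 16. The figures must match the rule adopted. State the tie convention beside them and, if ties go to the low-dose arm, use the step 4 values for each direction of superiority. State the over-run assumption: these figures take the stop as acting before either arm fills.

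At minimum, label 93% and 84% as applying to 16 per arm without the futility stop and with ties split.

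The change takes a few sentences and needs no extra patients or procedures. Its downside is that the stated probabilities become a few points less favourable.

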# Design:

Randomized phase 2 trial with the single stage selection design. Patients will receive either a constant low dose of pomalidomide (0.5 mg/day) for six months or a strategy of increasing dose of pomalidomide from 0.5 mg/d up through each individual patients' maximum tolerated dose, with escalations by 0.5 mg/d every 2 weeks to a maximum of 2.0 mg/d. As an early stopping rule for futility, if after 7 patients have enrolled on either arm, 0 have responded, then no further patients will be accrued to that arm as soon as this can be determined. To protect patient safety, an early stopping rule will be implemented. With two arms, each of which has a maximal accrual of 16 patients, up to 32 evaluable patients will be randomized. Response assessments will occur

**Abbreviated Title:** Pomalidomide for cGvHD **Version Date:** 4/29/2025

every 3 months with primary efficacy endpoint evaluated at 6 months. Patients with responding disease will continue therapy for another 6 months.

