## **3 STUDY IMPLEMENTATION**

#### 3.1 STUDY DESIGN

The study is a randomized phase 2 trial with the single stage selection design. It is known from prior trials that the maximum tolerated dose of pomalidomide is about 3 mg/d in persons with bone marrow disorders receiving prior therapies for cancer, in cGvHD doses <3mg/d have been well tolerated. This study will explore clinical toxicity of gradual escalation of pomalidomide doses <3 mg/d in subjects with cGvHD. Patients will receive either a constant low dose of pomalidomide (0.5 mg/day) for six months or a strategy of increasing dose of pomalidomide from 0.5 mg/d up through each individual patients' maximum tolerated dose, with escalations by 0.5 mg/d every 2 weeks to a maximum of 2.0 mg/d. In each of the two arms, the trial will use a single stage design.

As an early stopping rule for futility as outlined in section **8**, if after 7 patients have enrolled on either arm, 0 have responded, then no further patients will be accrued to that arm as soon as this can be determined. To protect patient safety, an early stopping rule will be implemented. With two arms, each of which has a maximal accrual of 16 patients, up to 32 evaluable patients will be randomized. Safety assessments and pregnancy testing for FCBP will be performed at scheduled intervals as described in the Study Calendar.

Response will be assessed every 3 months while taking pomalidomide following the criteria in Section 6.2. The primary efficacy endpoint will be evaluated at 6 months. Efficacy outcome is defined as clinical response (CR or PR) in subjects who enter the study with stable cGvHD or stable disease for  $\geq$ 3 mo for subjects with progressive cGvHD at study-entry. (Stability will be assessed by the clinician and by the clinical exam at the screening evaluation based on the clinician estimate of the disease trajectory during the 3 months pre-randomization). Subjects who meet the response criteria at 6 months will continue therapy for another 6 months. If in the subject's best interest, efforts will be made to provide access to study drug on compassionate basis beyond the 12-month study endpoint.

Patients who discontinue therapy for any reason will be followed for up to 24 months after starting pomalidomide as described in Section **6.1.3**.

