#### 6.2.2.1 Response Criteria

Efficacy will be assessed using NIH consensus criteria measuring for therapeutic response in clinical trials for cGvHD:

- **CR** is defined as complete resolution in all of signs and symptoms at all affected organs or tissues.
- **PR** is defined as improvement in ≥ 1 organ or tissue with no progression in any other affected organ or tissue. The calculations for PR and progressive disease (PD) are provided in Appendix H and Appendix I.
- **Response** < **PR** is defined as change towards improvement from the pre-treatment baseline but not meeting the criteria for CR or PR.
- **Stable Disease** is defined as no change in cGvHD, SD will be considered as response in patients with documented cGvHD progression over preceding 3 months.
- **Flare** is defined as exacerbation of cGvHD manifestations during withdrawal of immunosuppressive therapy which do not exceed those at the beginning of the trial and improves after reinstatement of previous treatment.
- **Progressive disease** is defined as failure of therapy to control cGvHD. The calculations for progressive disease (PD) are provided in Appendix I. Assessment by Organ-Specific Criteria. Patients who progress prior to 6 months evaluation will be also evaluable for the primary efficacy endpoint.
- **Mixed response** (improvement in some organs but worsening in others) will be categorized as progressive disease.

As outlined in Section **3.5**, type of involved organ, location and its measurements will be recorded at scheduled evaluations and reported on the appropriate CRF, equal to "Chronic GVHD Assessment (Clinician) Form," (Appendix G). All other measurements not being included in primary assessment but clinically related to cGvHD (e.g., change of pigmentation) will be reported in the source documents.

Skin and skin appendages: Skin assessments include 4 anatomic level of skin involvement:

- (1) erythematous rash (epidermal),
- (2) movable sclerosis (dermal),
- (3) non-moveable sclerosis, hidebound skin, or involvement of subcutaneous tissue and fascia (subcutaneous) and
- (4) ulceration (full thickness loss of epidermal tissue).

The first 3 measurements should be taken separately and recorded in metric notation using a body surface area (BSA). A cutaneous assessment worksheet for recording the BSA is provided (Appendix J). The size of ulcer should be measured the longest diameter (LD) of the largest ulcer.

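### The futility look counts only CR and PR, while the primary endpoint also counts stable disease in patients progressing at entry, so an arm can be closed despite having responders

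*Combined protocol and SAP*

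**What the plan says.** The futility rule is stated in general terms in three places. The Précis (Design) says "if after 7 patients have enrolled on either arm, 0 have responded, then no further patients will be accrued to that arm". Section 3.1 repeats the condition, "if after 7 patients have enrolled on either arm, 0 have responded", and Section 10 opens its futility paragraph in the same way. The next sentence of Section 10 says how the rule works in practice. It allows overrun, in that "patients may continue to be accrued beyond 7 in an arm", but registers no more patients on the arm "once the first 7 were evaluated and no PRs or CRs were identified in those first 7".

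Response itself is defined more widely. Section 3.1: "Efficacy outcome is defined as clinical response (CR or PR) in subjects who enter the study with stable cGvHD or stable disease for" at least 3 months in subjects whose disease was progressive at entry. Section 6.2.2.1: "SD will be considered as response in patients with documented cGvHD progression over preceding 3 months". Whether a patient entered stable or progressive is judged "based on the clinician estimate of the disease trajectory during the 3 months pre-randomization" (Section 3.1), and the Study Calendar records this trajectory at baseline.

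The main test in Section 10 uses 16 patients per arm, a 5% versus a 30% response rate, one-sided 0.10, and 3 or more responses as the success threshold. On selection it says that "if both arms are able to accrue to the full 16 patients, the arm with the greater number of responses will be selected".

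**The concern.** The general rule uses the word responded, which the protocol defines to include stable disease in patients progressing at entry. The only sentence that says how the rule is applied leaves stable disease out. The two readings disagree whenever the first 7 patients contain no CR or PR but at least one stable-disease response: one says continue, the other says close.

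Three things are at stake.

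- An arm could be closed although it has responders under the trial's own efficacy definition.
- Selection between arms is conditional on both reaching 16, so such a closure can also remove the comparison. Section 2.5 does provide for enrolment to continue on the remaining arm.
- It is unclear whether the 5% and 30% planning rates refer to CR/PR only or to the wider endpoint. That affects how 3 responses in 16 should be read, even if no arm closes.

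**Working it through.** **The plan's own figure.** With n = 16 and success at 3 or more responses, the exact binomial gives P(X ≥ 3 | p = 0.30) = 90.1% and P(X ≥ 3 | p = 0.05) = 4.3%. The stated 90% power reproduces and the type I error is within 0.10.

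**Inputs.** From Section 10: the first 7 patients, n = 16, threshold 3, rates 5% and 30%. Assumed, because the protocol does not give it: the share s of responses that come through stable disease, taken as 25%, 50% and 75%. The true response rate on the full definition is taken as p = 0.30.

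**Formulas.**
- CR/PR rate: c = p(1 − s).
- Closing condition as explained in Section 10: (1 − c)^7.
- Closing condition under the full definition: (1 − p)^7 = 0.70^7 = 8.2%.
- Closing condition met with at least one responder in the 7: (1 − c)^7 − 0.70^7.
- Closing condition met with k or more responders: (1 − c)^7 × P(Bin(7, q) ≥ k), where q = ps/(1 − c).

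For example, at s = 50%: c = 0.15, 0.85^7 = 32.1%, and 32.1% − 8.2% = 23.8% before rounding of the terms.

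| p = 30% | s = 25% | s = 50% | s = 75% | One definition |
|---|---|---|---|---|
| Closing condition met | 16.8% | 32.1% | 57.9% | 8.2% |
| … with ≥1 responder | 8.6% | 23.8% | 49.7% | 0 |
| … with ≥2 | 2.4% | 11.5% | 31.2% | 0 |
| … with ≥3 | 0.4% | 3.5% | 13.3% | 0 |

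**Power.** This depends on how many patients are already enrolled when the arm closes.

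- If accrual halts at 7 and every closed arm counts as a failure, power = P(Bin(16, p) ≥ 3) − (1 − c)^7 × Σx P(Bin(7, q) = x) × P(Bin(9, p) ≥ 3 − x).
- If N are enrolled at closure and 3 or more responses among them still count as success, add back (1 − c)^7 × Σx P(Bin(7, q) = x) × P(Bin(N − 7, p) ≥ 3 − x).

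| Power at p = 30% | s = 25% | s = 50% | s = 75% | One definition |
|---|---|---|---|---|
| Halt at 7, closed arm fails | 78.4% | 64.6% | 40.3% | 85.6% |
| 10 enrolled at closure | 81.6% | 76.2% | 69.6% | 85.9% |
| 13 enrolled | 86.2% | 84.4% | 82.2% | 87.7% |
| 16 enrolled | 90.1% | 90.1% | 90.1% | 90.1% |

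The fall from 90.1% to 85.6% in the last column comes from having any 0-of-7 look and is not due to the mismatch.

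**Inactive arm (5% on the full definition).** The closing condition is met with probability (1 − 0.05(1 − s))^7 = 76.5%, 83.8% or 91.6% as explained in Section 10, against 0.95^7 = 69.8% with one definition.

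**The case against.** The strongest reply is that the reference to PR and CR is loose shorthand. It appears once, in a sentence whose main purpose is to explain overrun, whereas the rule itself is stated three times in terms of responding, a word defined elsewhere. That is a plausible reading. But the sentence is offered as the meaning of the rule in practice, and it is the only one a study team could follow step by step. The ambiguity is therefore real.

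The second reply concerns size, and much of it stands.

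- **The shares are assumed.** At a 10% share, closure is 0.73^7 = 11.0%, of which 2.8 points involve a responder. The 75% column is an extreme.
- **Some overrun is likely**, because the primary evaluation is at 6 months. With 13 enrolled at closure, the mismatch costs 87.7 − 86.2 = 1.5 points of power at a 25% share and 87.7 − 84.4 = 3.3 at 50%.
- **The 30% may be the CR/PR rate**, with stable disease adding to it. Closure then stays at 8.2%. With total response assumed at 35%, 40% or 50%, halt-at-7 power is 89.2%, 90.8% or 91.7%, all above 85.6%. Closure with at least one responder still has probability 0.70^7 − 0.65^7 = 3.3%, 0.70^7 − 0.60^7 = 5.4%, or 0.70^7 − 0.50^7 = 7.5%.

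Third, a stricter interim look can be legitimate: it avoids relying on a clinician's estimate of prior trajectory, and it closes an inactive arm more often. That is true, but the protocol does not say it chose one.

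**Conclusion.** The concern holds. Section 10's working version of the futility rule does not match the response definition in Sections 3.1 and 6.2.2.1, and followed literally it can close an arm that has protocol-defined responders. This does not depend on any assumed share.

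The size does. If 30% is the full-definition rate and 25% to 50% of responses are stable-disease responses, the closing condition is met in 16.8% to 32.1% of cases instead of 8.2%. The power loss ranges from 85.6 − 64.6 = 21.0 points (50% share, accrual halted at 7) to none (all 16 already enrolled). If 30% is the CR/PR rate, closure is unchanged and there is no loss against the 85.6% comparator. The protocol does not settle which case applies, which is part of the defect. It should be fixed, and the correction is small.

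**What to change.** Reconcile Sections 3.1, 6.2.2.1 and 10 so that the futility look, the 3-of-16 test and the arm selection use one response definition. The simplest edit is to replace the reference to PRs and CRs in Section 10 with responses as defined in Section 3.1. At the same time, settle whether a stable-disease response requires a duration: Section 3.1 asks for at least 3 months and Section 6.2.2.1 gives none.

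If a CR/PR-only look is intended, say so and report its closure probabilities. In either case, state which definition the 5% and 30% rates refer to, and whether a closed arm with 3 or more responses among patients already enrolled counts as a success.

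The cost is one or two sentences in Section 10 plus the matching of definitions; no new data are needed. The downside of a single, wider definition is fewer closures of an inactive arm: at a 5% true rate, closure falls from 76.5%, 83.8% or 91.6% (shares of 25%, 50%, 75%) to 69.8%. The look would also rest partly on the clinician's judgement of prior trajectory, as the primary endpoint already does.
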